7.7. Postoperative Management and Instruction

The physician will provide normal standard of care after implantation of the system, including standard post-operative monitoring. Instructions for wound care and monitoring will be provided to the patient by the implanting physician. Patients will be informed to report any adverse events or changes in medication to study personnel. Patients will be informed not to manipulate the leads after implantation because tissue erosion may occur. The patient will be sent home for a 2-3 week recovery period to let any swelling and/or post-operative pain subside prior to activation of SCS system, unless otherwise

determined by the installing investigator. During this time, the device may not be activated and the patient may not be provided with the Patient Programmer. Prophylactic antibiotic therapy may be instituted at the discretion of the Investigator.

If the leads migrate during the study, the implanting physician will examine the area of implantation. The leads can be repositioned or re-implanted if mutually agreed upon by the physician and the patient. The patient and the implanting physician will make the mutual decision about any possible revision of the device based upon what is medically safe, what is desired by the patient, and what is in the patient's best medical interests.

If an infection occurs, standard medical practice suggests that the leads be removed and the patients undergo a standard course of oral antibiotics. Any infection or wound will be given time to heal before any re-implantation is attempted.

If the device is completely explanted from the study patient for any reason and re-implantation is not an option, then the patient will exit the study.

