7.11.2. Adverse Events

Adverse events will be collected according to the section below. Outcomes will be in percentage of patients experiencing events and total number of events, and will be stratified by severity, type, and resolution.

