The Pain Location Form includes a map of the body that is labeled with different numbered regions. The patient is instructed to shade in or place an X in the area the patient is feeling pain.

Paresthesia Coverage Form

The Paresthesia Coverage Form includes a map of the body that is labeled with different numbered regions. The patient is instructed to shade in or place an X the area the patient is feeling stimulation/paresthesia. Patients will also indicate which area(s) of pain relief has given them the greatest improvement over their daily activities. This form looks similar to the Pain Location Form so it should be made clear to the patient that one is for pain and one is for paresthesia.

8. Adverse Events (AEs)

Adverse events are solicited at every study visit throughout the duration of the study. Adverse events will also be solicited at any unscheduled visits that occur.

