8.3. Reporting AEs

Throughout the course of the proposed study, all device and/or procedure-related adverse events will be recorded and monitored by the Investigator(s) at each participating site. Additionally, any serious adverse events observed by the investigator or reported by the patients, whether or not ascribed to the device or procedure will be recorded. Non-device/procedure-related adverse events including but not limited to common cold, other bodily pain (such as dental or neck pain) or elective outpatient surgery with hospitalization less than 24 hours will not be recorded.

Only adverse events that occur during or after system implantation will be collected. Every effort will be made to remain alert to possible adverse experiences and unexpected findings. If adverse experiences occur, the first concern will be the safety of the patient and appropriate medical intervention will be made.

Individual reports of device and/or procedure-related adverse events and all serious adverse events should be documented and reported appropriately on the adverse event case report form. An investigator shall submit to the IRB a report of any unanticipated adverse effect (UADE) occurring during the investigation as soon as possible, in accordance with IRB policies.

The Investigator must report all SAEs (e.g. unanticipated death or serious injury require hospitalization greater than 24 hours) to the IRB as soon as possible, in accordance with IRB policies. This notification can occur by email, telephone, or fax and the site will forward the completed AE form as soon as it is available.

The Investigator must also promptly report the resolution to all reported serious, unanticipated, or device/procedure-related AEs. Non-serious adverse events should be reported at the next routine contact.

All AEs shall also be reported to SJM and reviewed on a monthly basis. All SAEs will be submitted to the FDA by SJM immediately upon receipt. All AEs will be reviewed on a quarterly basis by SJM per their own standard operating procedures.

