8.4. Anticipated Adverse Events and Complications

Complications and anticipated adverse effects associated with SCS implantation include but are not limited to:

- Stimulation at high outputs may cause unpleasant sensations or motor

disturbances, including involuntary movement. If either occurs, turn off your IPG immediately.

- Undesirable changes in stimulation may occur over time. These changes may be related to cellular changes in tissue around the electrodes, changes in electrode position, loose electrical connections, and/or lead failure.
- Stimulation may occur in unwanted places, such as the radicular (nerve root) chest wall area
- A lead can move and result in changes in stimulation and/or a reduction in pain relief
- Placement of a lead in the epidural space may cause epidural hemorrhage, hematoma, infection, spinal cord compression, and/or paralysis
- Cerebrospinal fluid (CSF) leakage is possible
- Paralysis, weakness, clumsiness, numbness, and/or pain below the level of the implant can occur
- Persistent pain may occur at the electrode or IPG site
- Seroma (mass or swelling) may occur at the IPG site
- Implant materials may cause an allergic or rejection response
- The implant can move, or skin can erode from around it
- Battery failure and/or battery leakage is possible

IPG Complications

Changes in stimulation parameters may occur due to the failure of, or changes in, components over time, which results in:

- Understimulation
- Return of underlying symptoms
- Overstimulation
- Premature battery depletion, and
- The need to explant the device

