10.6. Data Sets

All patients who complete the 6 week follow-up appointment and questionnaires will be included in the analysis.

Patients with missing baseline values will be excluded from the analysis. Missing data pertaining to adverse events will not be imputed.

11. Withdrawal of Patients from Study

Withdrawal is defined as a patient’s termination of participation from a clinical study. Patients may be discontinued from the study at any time. The reason for discontinuation will be recorded

on the Exit and Withdrawal form. Discontinued patients may not be replaced in the study. Prior to discontinuing a patient, every effort should be made to contact the patient in an effort either to get the patient back into compliance with the protocol, or to obtain as much follow-up data as possible. Reasons for discontinuation include, but are not necessarily limited to:

- Voluntary withdrawal by the patient;
- Patient is Lost to Follow-up: Patient will be considered “lost to follow-up” after a minimum of 2 documented phone calls by personnel at the investigational center to the patient or emergency contact and a certified letter was sent to the last known address.
- Investigator may discontinue the patient’s participation in the study for reasons including but not limited to: patient noncompliance, surgical revision not appropriate, unwillingness or inability to cooperate with study requirements (therapy regimen, follow-up visits, etc.).

12. Modification of Protocol

Any amendments to this protocol must be prepared by the Coordinating Investigator and approved by the appropriate regulatory agencies and the local authority (IRB) before implementation by the Investigator.

13. Discontinuation of Study

The Clinical Coordinating Investigator reserves the right to discontinue any study at any time for administrative reasons, such as but not limited to, a decision to discontinue further clinical Investigations with the devices, improper conduct of the study by the Investigator, inability to obtain the number of patients required by the protocol, etc.

If the study is prematurely terminated or suspended, it is the responsibility of the investigator to promptly inform the patients and assure appropriate therapy and follow-up. The Investigator must also adhere to local IRB requirements and reporting of study termination or discontinuation.

14. References

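### Study exit after a final explant ends planned safety follow-up, and the plan does not say how event totals and resolution are then completed

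*Combined protocol and SAP*

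**What the plan says.** Section 7.7 sets two conditions, complete explant for whatever reason and no option to re-implant ("If the device is completely explanted from the study patient for any reason and re-implantation is not an option"), and then makes exit mandatory: "re-implantation is not an option, then the patient will exit the study". It gives no time for the exit and no contact after it. For infection the same section allows an interval first: "Any infection or wound will be given time to heal before any re-implantation is attempted".

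Section 11 defines withdrawal as the end of participation. Among the reasons for which an investigator may discontinue a patient it lists "patient noncompliance, surgical revision not appropriate, unwillingness or inability to cooperate with study requirements". It asks for every effort to collect follow-up data, but before discontinuation; it plans nothing afterwards.

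Section 8 ties safety data to visits: "Adverse events are solicited at every study visit throughout the duration of the study", and also at unscheduled visits. Section 8.3 then requires an outcome for each such event: "The Investigator must also promptly report the resolution to all reported serious, unanticipated, or device/procedure-related AEs". It makes no exception for patients who have left and sets no end date. Section 7.11.2 reports both the percentage of patients with events and the total number of events, and says that these outcomes "will be stratified by severity, type, and resolution".

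Section 10.1 places the primary analysis at 24 weeks. Section 10.3.2 tests the percentage of patients with an adverse event, and section 10.3.3 the percentage with a revision. Section 10.6 limits the analysis to patients who complete the 6-week visit and its questionnaires.

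**The concern.** Safety is half of the primary objective, and the number and type of adverse events is a primary variable (sections 2.1 and 2.3). Under section 7.7 the length of safety observation depends on device removal, which is often a consequence of a complication. Section 8.4 lists some that could lead there: "Placement of a lead in the epidural space may cause epidural hemorrhage, hematoma, infection, spinal cord compression, and/or paralysis". Once the patient has left, routine solicitation stops. A further infection, another operation or a lasting deficit need not come to the study's notice, and an event still open at exit may have no recorded outcome.

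The comparison between methods is exposed as well. The study is unblinded (section 7.9), each investigator uses only one method (section 3.1), and decisions about revision are shared between physician and patient (section 7.7). The readiness to declare re-implantation not an option, or revision unsuitable, may therefore differ by arm, and with it the completeness of the safety data.

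**Working it through.** **1. The passages side by side.**

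| Question | Section | Answer in the plan |
|---|---|---|
| When must a patient leave? | 7.7 | After complete explant, any cause, if re-implantation is not an option |
| When may a patient be discontinued? | 11 | Among others, if surgical revision is not appropriate |
| When are adverse events solicited? | 8 | At study visits and unscheduled visits |
| What is arranged after exit? | 7.7, 11 | Nothing; section 11 asks for effort before discontinuation only |
| Which outcomes are owed? | 8.3 | Resolution of all reported serious, unanticipated or related events |
| What is reported? | 7.11.2 | Patients with events, total events, and both by severity, type and resolution |
| Who is analysed? | 10.6 | Those who complete the 6-week visit and questionnaires |

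The duty in 8.3 continues after exit, but no visit, call or form is assigned to carry it out.

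**2. Which measures are affected.**

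- *Total events and resolution (7.11.2):* incomplete for any patient who exits before 24 weeks.
- *Percentage of patients with an event (10.3.2):* if an adverse event was recorded before exit and the patient is in the analysis set, the patient already counts, and later events change nothing. The rate is affected if the explant was not preceded by a recorded adverse event, so that a later first event is missed, or if the patient exits before the 6-week visit.
- *The 6-week condition:* activation is about 2 to 3 weeks after implantation (7.8), and the visit is 42 ± 7 days after activation (Table 1). Nominally this is 2 + 6 = 8 to 3 + 6 = 9 weeks after implantation. A patient who exits earlier is not analysed under 10.6, so even the event that led to the explant is not counted.

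**3. How many patients.** The plan gives no rate of explant without re-implantation, so there is no figure to reproduce, and the sample size of 50 does not depend on one. The nearest input is the infection rate in Table 2 (section 10.2): 4.5% non-awake and 6.0% awake. Arms are 25 each for 50 patients at 1:1 (10.2), or 30 each at the cap in section 6.

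Expected infections = n × 0.045 + n × 0.060:

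- n = 25: 1.125 + 1.5 = 2.625, about 2.6
- n = 30: 1.35 + 1.8 = 3.15, about 3.2

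Let f be the share of infections that end in final explant. This is an assumption; the documents do not give it. Expected exits = f × expected infections. Chance of at least one = 1 − (1 − 0.045f)^n × (1 − 0.060f)^n.

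| f | Exits, n = 25 | At least one | Exits, n = 30 | At least one |
|---|---|---|---|---|
| 25% | 0.7 | 48% | 0.8 | 55% |
| 50% | 1.3 | 74% | 1.6 | 80% |
| 100% | 2.6 | 93% | 3.2 | 96% |

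If f is zero, so are the exits from this cause. Explants for other causes would add to the count; the documents give no figure for them. In an arm of 25, one patient is 1/25 = 4 percentage points of a patient-level rate.

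**The case against.** The strongest reply is that the plan is not inconsistent. A reader might infer that 7.7 contradicts 8.3, but the text does not go that far: the duty in 8.3 covers every reported event of the listed kinds, is not confined to active participants and has no end date. An investigator can record the exit and still report the resolution. That stands. What is missing is the means, and 8.3 covers only events already reported, not new ones.

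A reader might also infer that follow-up stops at the most severe complications. The documents do not support this. The rule covers explant for any reason, including causes that are not severe, and a severe event without final explant leaves the patient in follow-up. Nor need exit fall on the day of explant. Since healing precedes any re-implantation, part of the resolution may be seen first, so counting all the weeks from explant to week 24 as lost would overstate the gap. Section 8.1 also limits procedure-related events to 30 days after the procedure, so what remains at risk later is serious events, device-related events and the sequelae of any further surgery.

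Third, the tested endpoints are patient-level percentages, and section 10 has no test of event totals or resolution. For an analysed patient whose explant followed a recorded event, the test is untouched. This stands and confines the effect mainly to descriptive results. Those are still outcomes that the plan names, and in arms of 25 to 30 a few truncated cases can matter to them.

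Last, infections are not exits. Section 7.7 speaks of removing leads in infection, not of complete explant without re-implantation. The chance of an infection must not be read as the chance of an exit, which is why the share f is shown as a range.

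**Conclusion.** The gap is real and modest. Sections 7.7 and 11 end participation after a final explant, or where revision is judged unsuitable, without planning any later safety contact, while 8.3 and 7.11.2 depend on outcomes that may come later. The passages are unreconciled, not contradictory. Event totals and resolution bear most of the effect. The patient-level adverse event rate is affected only in the two situations in the working: no recorded event before explant, or exit before the 6-week visit.

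On infections alone, 0.7 to 2.6 exits are expected in 50 patients if 25% to 100% of them end in final explant. That share is assumed, the Table 2 rates are planning values from retrospective studies, and the true number of exits is unknown. A reader might infer that the method with more severe complications will look safer. That direction is possible, since exit practice may differ by arm, but the documents give nothing from which to establish or size it. The change is worth making because it is cheap and the data cannot be recovered afterwards.

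**What to change.** - **Sections 7.7 and 11:** state that a patient whose system is finally explanted, or for whom revision is judged unsuitable, stops device-dependent assessments (programming, paresthesia coverage). The patient stays in follow-up for adverse events, additional surgery and medication to the 24-week time point, and beyond it while a serious or related event is still open, unless consent is withdrawn.
- **Section 10.6:** state that these patients are included in the adverse event and revision analyses even without a completed 6-week visit. Without this, a patient who exits early would be followed but still not counted.

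The Adverse Event, Additional Surgery and Medication forms in Appendix A already exist, and contact can be by scheduled visit or telephone. The cost is longer follow-up for probably a few patients and perhaps slightly higher adverse event totals. No rule on explant, treatment or re-implantation changes.

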7.8. Device Activation

The permanent system device activation visit will occur approximately 2-3 weeks after permanent system implantation. At this visit, each patient will have their device programmed to comparable individualized programming parameters. All patients will receive a Patient Programmer that will enable him/her to activate the ON and OFF positions and adjust amplitude within the prescribed range.

A map of paresthesia coverage is collected along with final programmed parameters, lead impedance, and device data. Any changes in medications are noted as well.

7.8.1. Programming Parameters

The programming ranges are defined below to use as a guide for consistency in study programming. Ranges are provided due to differences in patient perception. Programming may vary in cases where coverage is difficult to obtain or the patient experiences uncomfortable stimulation.

- Patients will be stimulated at supra-sensory threshold levels using Spinal Cord Stimulation leads (i.e. leads placed in the epidural space). Typical parameter ranges are pulse width of 150-350 μ s and frequency of 20-80 Hz. Amplitude will be programmed according to individual patient perception and comfort and to a level that produces paresthesia for the patient.
- Patient Global Impression Form
Patient satisfaction with permanent implant procedure will be assessed on a 5 point Likert scale. Patients will be asked to rate their satisfaction as very satisfied/ satisfied/ neither satisfied nor dissatisfied/ dissatisfied/ very dissatisfied as compared with their trial implantation procedure.

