Randomization:	There will be no randomization of the patients. Patients recruited and enrolled at St. Luke's Neurological Associates or Thomas Jefferson University will undergo implantation under general anesthesia with EMG neuromonitoring for testing of the distribution of induced paresthesia ("non-awake"). Patients recruited and enrolled at Geisinger or Milton S. Hershey Medical Centers will undergo implantation of the device in an awake operation with local anesthetic and patient interaction for testing of the distribution of the induced paresthesia ("awake").
Statistical Analysis:	The primary endpoints will be procedure time, rates of adverse events, specifically lead revisions, and patient satisfaction. An additional endpoint will be the proportion of painful regions covered by paresthesia in non-awake compared to awake patients
Adverse Events	All device/procedure-related and all serious adverse events that occur and are volunteered by the patient and solicited by the site staff will be collected.

1. Introduction

Spinal cord stimulation (SCS) is an adjustable, non-destructive, therapy in which an electrical current is applied to the spinal cord for management of neuropathic pain. Leads are placed in the epidural space, which apply electrical stimulation to the spinal cord. It has been used for many years and has proven to be effective in the treatment of chronic, intractable pain including failed back surgery syndrome CRPS, phantom limb pain, cancer pain, peripheral vascular disease, and ischemic limb pain (Burchiel et al., 1996; Cameron, 2004; Kemler, de Vet, Barendse, van den Wildenberg, & van Kleef, 2008; Khan, Raza, & Khan, 2005; Turner, Loeser, Deyo, & Sanders, 2004).

The success of the therapy relies on the ability to create an overlap between the pain areas and the device-induced paresthesia. Lead placement has historically been done under awake conditions, using direct feedback from the patient in order to define adequate paresthesia coverage. The awake operation is performed while the patient is under local anesthesia, which is very stressful for the patient and predisposes them to movement. This can lead to decreased patient satisfaction, equipment migration, undesired stimulation effects, and treatment failure.

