2.5. Additional Data

- Demographics: gender, age, height, weight, ethnicity, marital status
- Pain history: primary diagnosis, pain duration, pain etiology, prior treatments
- Medication usage including rescue medication
- Pain quality as assessed by the Short-Form McGill Pain Questionnaire version 2
- Quality of life as assessed by EuroQol (EQ-5D) generic health index questionnaire
- Patient global impression of satisfaction with device implantation compared to trial system implantation.
- Surgery and device information
- Programming data
- Patient reported perception of pain relief.
- Responder classification for average daily overall pain. Responders are classified as patients with $\geq 30\%$ or $\geq 50\%$ reduction in pain.

3. Study Design

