3.1. Design

This is a post-market, prospective, multicenter, parallel designed, non-randomized, non-blinded, 6-month study. A minimum of 50 patients will be implanted from up to 4 active sites, coordinated by a single lead investigator.

Patients who have had a successful SCS trial and are indicated for permanent implantation will be approached to participate in this study prior to permanent implantation. Patients will be recruited and enrolled by physicians at any one of the involved sites. Each Investigator will only use one method (awake or non-awake) according to his/her typical practice. Patients will receive treatment from their enrolling physician.

[figure not shown]

Table 1: Study Schedule

Timing of visit	Activities at visit	Case Report Forms
Screening and Informed Consent (may be immediately after Trial System Explant)	Patient evaluated for eligibility Patient signs informed consent Schedule patient for baseline evaluation at treatment site	Enrollment Form Inclusion/Exclusion Criteria Form
Baseline Evaluation 7-28 days after screening	Patient completes questionnaires Complete history and physical exam Record current medication use Collect patient reported data	Baseline Self Evaluation Form Pain Location Form Pain Evaluation Form SF-MPQ-2 (Pain Quality) EQ-5D (Quality of life) Medication Form
Permanent System Implantation	Permanent system implantation Record any complications Record any changes in medication Discourage activation at discharge Save digital recording or EMG recording if system permits.	Surgery Form Adverse Event Form Programming Form (if programmed at discharge) Medication Form
Initial Programming Visit	Record any complications Record any changes in medication Provide patient with the patient programmer and charging system Record patient's global impression of satisfaction with the implant procedure.	Programming Form Paresthesia Coverage Form Patient Global Impression Form Medication Form
6 weeks 42 ± 7 days after activation	Record any complications Record any changes in medication Patient completes questionnaires Modify programming parameters (if necessary) Collect patient reported data	Follow-up Visit Form Pain Evaluation Form Pain Location Form Programming Form SF-MPQ-2 (Pain Quality) EQ-5D (Quality of life) Paresthesia Coverage Form Medication Form

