5.1. Inclusion Criteria

Patients enrolled in this study must meet the following inclusion criteria:

1. Patient is able to provide informed consent to participate in the study
2. Patient is 18 years of age or older
3. Patient has had a successful trial system and is presenting for permanent implantation of a paddle electrode in thoracic region.
4. Patient is willing to cooperate with the study requirements including compliance with the treatment regimen and completion of all office visits

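### The satisfaction item pairs absolute answers with a comparison to the earlier trial implantation, so it measures satisfaction with the placement method ambiguously and with possible confounding

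*Combined protocol and SAP*

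**What the plan says.** Section 7.8.1 first gives the target of the Patient Global Impression Form: "Patient satisfaction with permanent implant procedure will be assessed on a 5 point Likert scale". The next sentence gives the answers and a reference point: "very satisfied/ satisfied/ neither satisfied nor dissatisfied/ dissatisfied/ very dissatisfied as compared with their trial implantation procedure". Section 2.5 lists the same variable with the same reference: "Patient global impression of satisfaction with device implantation compared to trial system implantation". Table 1 in Section 3.1 gives the task for the initial programming visit without any reference: "Record patient's global impression of satisfaction with the implant procedure".

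The form is completed once. Appendix A marks it at Initial Programming only, and Section 7.8 sets the timing: "The permanent system device activation visit will occur approximately 2-3 weeks after permanent system implantation". No section says whether it comes before or after the device is programmed.

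On the reference procedure, the plan requires only that it succeeded: "Patient has had a successful trial system and is presenting for permanent implantation of a paddle electrode in thoracic region". Its anaesthesia and technique are not specified, and no listed data item explicitly records them. Arms are set by enrolling site (Protocol Summary; Section 6).

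The status of satisfaction varies. The Protocol Summary states: "The primary endpoints will be procedure time, rates of adverse events, specifically lead revisions, and patient satisfaction". Section 2.3 does not list it among the primary variables, Section 2.5 places it under additional data, Sections 10.3 and 10.4 give it no hypothesis or test, and Section 10.5 promises summary statistics for additional data.

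**The concern.** The Introduction argues that awake surgery is hard on patients and can lower their satisfaction, and it offers comfort as a possible advantage of the non-awake method. This form is the only listed measure of satisfaction with the procedure, so it carries that part of the comparison.

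Three features make the answer hard to interpret.

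- **Scale and reference do not match.** None of the answers means better, same or worse, yet the patient is told to compare. Some will rate the permanent procedure on its own and others will rate the change from the trial procedure. The completed form does not show which.
- **The reference is outside the study's control.** For patients who answer comparatively, the arm contrast becomes permanent minus trial at one pair of sites against permanent minus trial at the other pair. Any difference in local trial practice falls on the arm comparison, and there is no randomisation to balance it.
- **Timing is open.** The rating of the operation may be given after programming at that visit, so the quality of stimulation may colour it. Paresthesia coverage is itself the secondary outcome.

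At stake is whether a between-arm difference in satisfaction, or its absence, can be read as being about the placement method.

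**Working it through.** The plan gives no figure for satisfaction to reproduce: Table 2 in Section 10.2 has no satisfaction row. The check compares the descriptions and then asks under what conditions the ambiguity would produce a spurious arm difference.

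**1. The descriptions side by side**

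| Place | What is rated | Compared with the trial procedure? |
|---|---|---|
| 7.8.1, first sentence on the form | Permanent implant procedure | No |
| 7.8.1, second sentence | Same, five absolute answers | Yes |
| 2.5 | Device implantation | Yes |
| 3.1, Table 1 | Implant procedure | No |

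Two constructs are described for one item: a stand-alone rating and a change from the trial procedure.

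**2. Size of the ambiguity for one patient**

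Score the answers 5 (very satisfied) to 1 (very dissatisfied); this scoring is an assumption. A patient satisfied with both procedures, and equally so, scores 4 on the stand-alone reading and 3 on the comparative reading. The gap is 4 − 3 = 1 category.

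**3. What that does to an arm contrast**

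Suppose every patient is equally satisfied with both procedures, and shares pA and pB of the two arms read the item comparatively. Then:

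spurious mean difference = (pA − pB) × (4 − 3)

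- 50% v 20%: 0.30 × 1 = 0.3 category
- 50% v 0%: 0.50 × 1 = 0.5 category
- equal shares: 0

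All shares are assumptions. The plan offers no reason why they should differ by arm.

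**4. What a difference in trial experience would do**

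Inputs: 25 per arm (minimum of 50, enrolled 1:1, Section 10.2). Latent score = permanent experience − w × trial experience, each with SD 1, cut into five categories at −1.5, −0.5, 0.5 and 1.5. Permanent experience is identical in the two arms; mean trial experience differs by d SD. The yardstick is a Mann-Whitney test at 5%, with 3,000 simulated studies per cell. The plan names no test for this item, and w and d are assumed.

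Standardised shift between arms = w × d / √(1 + w²). For example, w = 1 and d = 1 gives 1/√2 = 0.71.

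| w (weight on trial procedure) | d | Standardised shift | False-positive rate |
|---|---|---|---|
| 0 (reference ignored) | 0 to 1.0 | 0 | 4.6% to 5.4% |
| 0.5 | 0 | 0 | 4.4% |
| 0.5 | 0.25 | 0.11 | 6.1% |
| 0.5 | 0.5 | 0.22 | 11.2% |
| 0.5 | 1.0 | 0.45 | 31.1% |
| 1 (fully comparative) | 0 | 0 | 4.5% |
| 1 | 0.25 | 0.18 | 9.3% |
| 1 | 0.5 | 0.35 | 21.3% |
| 1 | 1.0 | 0.71 | 62.7% |

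The arm with the better trial experience scores lower, so the direction depends on a difference the documents do not give.

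**5. Timing**

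For the initial programming visit, Table 1 names handover of the patient programmer before the satisfaction rating, and lists the Programming and Paresthesia Coverage forms before the satisfaction form. That is a listing, not an instructed sequence. It leaves either order open.

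**The case against.** The strongest reply is that the item works well enough. It names the permanent procedure as its target and is given in both arms at the same visit, so the arms can be compared. Using each patient's own earlier procedure as an anchor is a defensible way to reduce differences in rating style, and its repetition in Section 2.5 suggests it was deliberate. Section 7.12 has patients ask about anything unclear and has staff review completed questionnaires. The form itself is not reproduced in the documents, so its wording or instructions may be clearer. Satisfaction also has no test in Section 10.

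Much of this stands, and it rules out three stronger readings.

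- A reader might infer that the item does not measure satisfaction with awake versus non-awake placement at all. The documents do not support that: an ambiguous measure is not an empty one.
- A reader might infer that the arm contrast is biased. Nothing in the documents says that trial procedures, or the reading of the item, differed between the two groups of sites. If neither differs, the ambiguity adds noise but no systematic shift.
- A reader might infer that patients' first experience of paresthesia contaminates the rating. Every patient has already had a successful trial system, awake-arm patients are test-stimulated during surgery (Section 7.6.1), and Table 1 allows for programming at discharge. What remains is that the quality of stimulation at this visit may colour the answer.

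The mismatch itself survives. An anchor of this kind needs comparative answers, and Section 7.8.1 specifies absolute ones. The general instruction in Section 7.12 does not say which reading is intended. Giving satisfaction only summary statistics does not cure the problem, because a descriptive comparison carries the same ambiguity. The conflict over endpoint status is a separate matter; it affects how much weight this item bears.

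**Conclusion.** The concern holds in limited form. As specified, the item is an ambiguous and potentially confounded measure of satisfaction with the assigned placement method. The ambiguity is worth one category for a patient equally satisfied with both procedures, and the completed form does not allow it to be resolved afterwards.

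Whether there is bias, and its direction and size, cannot be determined from the documents. Bias between arms needs trial experience, reading of the item, or the influence of programming to differ between arms. The 0.3 to 0.5 category shifts and the false-positive rates of about 6% to 63% rest wholly on assumed differences; without such differences the result is zero shift and a rate near 5%.

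The change is worth making because it is cheap, the item is the only listed measure of procedural satisfaction, and the Protocol Summary calls it primary. Sections 2.5 and 10.5 give it a lesser role, so it should not be presented as undermining the study's main conclusions.

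**What to change.** 1. Ask for satisfaction with the permanent implant procedure itself, on the existing 5-point scale and with no reference to the trial procedure. Use this item for the between-arm comparison.
2. Keep the trial comparison as a separate item with comparative answers, from much better to much worse.
3. State that both items are completed at the initial programming visit before the device is programmed. Patients already programmed at discharge can be identified from the Programming Form that Table 1 provides for that case.
4. Align Sections 2.5, 3.1 (Table 1) and 7.8.1 so that they describe the same two items.

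The cost is one extra question and one sequencing sentence on an existing form at an existing visit, made through the amendment route in Section 12. Forms already completed must be reported separately, since they cannot be assigned to either new item. The change removes the dependence on the trial procedure from the main comparison. It does not remove differences between sites, which remain because the arms are defined by site and patients are not randomised.
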